12.1 Extent of Exposure

The summary statistics will be produced using intervention fidelity measures given in section 10.4.

12.2 Adverse Events

Descriptive summary statistics for adverse events (AEs) during the baseline visit will be reported. The number of AEs during baseline and the frequencies (number and percentage) of participants with one or more AEs will be summarized by treatment group and overall.

In accordance with clinicaltrials.gov reporting requirements, the following table summarizing adverse events is required and will be provided:

- Other (Not Including Serious) Adverse Events: A table of anticipated and unanticipated events (not included in the serious adverse event table) that exceed 5% within either treatment group, grouped by organ system, with number and frequency of such events in each treatment group.

The summary statistics will be produced in accordance with section 10.

12.3 Deaths, Serious Adverse Events and other Significant Adverse Events

Descriptive summary statistics for serious adverse events (SAEs) during baseline will be reported. The number of SAEs during baseline and the frequencies (number and percentage) of participants with one or more SAEs during baseline will be summarized overall, by treatment group, and by body system.

A subject listing of all SAEs during baseline, SAEs during baseline causing study discontinuation, and deaths will be presented.

In accordance with clinicaltrials.gov reporting requirements, the tables below summarizing deaths and SAEs are required:

- All-Cause Mortality: A table of all anticipated and unanticipated deaths due to any cause, with number and frequency of such events in each treatment group.
- Serious Adverse Events: A table of all anticipated and unanticipated serious adverse events, grouped by organ system, with number and frequency of such events in each treatment group.

The summary statistics will be produced in accordance with section 10.

12.4 Pregnancies

No relevant measures are collected as part of the CAPTURE study.

12.5 Clinical Laboratory Evaluations

No relevant measures are collected as part of the CAPTURE study.

12.6 Prior and Concurrent Medications

Prior relevant medications are summarized as baseline variables in section 10.3:

- Use of rescue respiratory medication (Yes if participant uses at least one short-acting bronchodilator, No, or Not Reported)
- Use of maintenance respiratory medication (Yes if participant uses at least one of the following: LABA, LAMA or anti-inflammatories, No, or Not Reported)
- Use of supplemental oxygen (Yes, No, or Not Reported)

12-month follow-up assessments record new prescriptions for respiratory medication after the baseline visit (long acting bronchodilator, inhaled steroids, oral anti-inflammatory), vaccination status, and in smokers, a new prescription for smoking cessation medication

12.7 Other Safety Measures

No additional safety measures are collected as part of the CAPTURE study.

13 Other Analyses

13.1 SARS-COV-2 Impact on Study Enrollment, Follow-up and Power

We have performed additional analyses for the CAPTURE DSMB regarding the impact of SARS-COV-2 on study power for the cluster randomized clinical trial described in Aim 3 of the CAPTURE protocol, summarized in a Memo dated March 30, 2020. Sections of the memo relevant to the SAP are repeated below.

At the time of placing enrollment on hold, the CAPTURE study was ahead of enrollment projections with a goal of completion of all patient enrollment by January 31, 2021. Table 1 displays enrollment data for each of the CAPTURE study's six enrolling PBRNs as of March 19, 2020, the date the last of

the six PBRNs temporarily stopped enrollment.

Table 6.

| PBRN site | Date enrollment put on hold | Number of practices enrolled as of 19MAR2020 (goal) | Number of patients enrolled as of 19MAR2020 (goal) | Estimated date of resumption of enrollment |
|-----------|-----------------------------|---|--|--|
| A | 13MAR2020 | 15 (20) | 663 (1000) | Indeterminate |
| B | 16MAR2020 | 15 (20) | 750 (1000) | Indeterminate |
| C | 16MAR2020 | 9 (20) | 431 (1000) | Indeterminate |
| D | 19MAR2020 | 6 (8) | 280 (400) | Indeterminate |
| E | 13MAR2020 | 11 (20) | 468 (1000) | Indeterminate |
| F | 16MAR2020 | 12 (13) | 446 (650) | Indeterminate |

As of April 1, 2020, none of the sites has an estimate of when enrollment will be able to resume. This information will be added as soon as such information becomes available.

Projected Enrollment Impact

To facilitate planning, projections on patient and practice enrollment impacts for Aim 3 have been developed. These projections are based on several assumptions.

1. Monthly enrollment rates of 100 or 125 patients as continuation and 5 new practices enrolled per month, consistent with prior data.
2. Two, four and six-month delays in enrollment.

Table 7.

| Enrollment suspension length assumption | Enrollment re-start date | Enrollment rate/month | Total number of participants (practices) enrolled by 31JAN2021 | Total number of participants enrolled by 31MAR2021 |
|---|--------------------------|-----------------------|--|--|
| 2 months | 1-Jun-20 | 100 | 3850 (100) | 4050 |
| 4 months | 1-Aug-20 | 100 | 3650 (100) | 3850 |
| 6 months | 1-Oct-20 | 100 | 3450 (90) | 3650 |
| 2 months | 1-Jun-20 | 125 | 4050 (100) | 4300 |
| 4 months | 1-Aug-20 | 125 | 3800 (100) | 4050 |
| 6 months | 1-Oct-20 | 125 | 3550 (90) | 3750 |

We evaluated other scenarios including being able to increase enrollment to 150 patients per month with delays of two, four and six months and ending enrollment in January 2021 and March 2021.

Impact on Follow-up

The tables below present information on the initiation dates of the 12-month medical record abstraction by PBRN and the information on 12-month patient survey follow up as of March 25, 2020.

Table 8. 12-month Medical Record Abstraction (As of March 19, 2020)

| PBRN Site | Original ideal date of starting for 12- month medical records abstraction |
|-----------|---|
| A | 23MAR2020 |
| B | 30MAR2020 |
| C | Unknown |
| D | Unknown |
| E | 06APR2020 |
| F | No eligible patients until September 2020 |

Table 9. 12-month Patient Survey – COPD Foundation As of 3/25/2020

| | |
|---------------------------|-----------|
| Number Eligible | 380 |
| Phone Only | 118 |
| Email | 256 |
| Mail Only | 6 |
| Completed 12 Month Survey | 248 (65%) |
| Web | 84 |
| Phone | 134 |
| Mail | 30 |
| Mailed Surveys | 120 |
| Lost to Follow-Up | 20 |

Since all surveys are done by email, telephone call or mailings, there are no planned disruptions of the 12-month follow up patient surveys. All staff triggering email surveys, making telephone calls or preparing mailings are working from home.

Impact on Power

The goal of Aim 3 is to define the impact of CAPTURE information provided to clinicians in identifying and managing patients with respiratory symptoms (CAPTURE+) across a broad range of primary care settings. This Aim depends on the overall number of patients identified who are CAPTURE+, the number of practices enrolled as well as the ability to complete longitudinal follow-up.

Calculations were performed assuming 10 CAPTURE+/practice based on 67 total practices with > 1 CAPTURE+ patients (actual current state) taking into account loss of power due to variable cluster sizes. These data suggest that we are on track for having a well powered study for the primary analysis, even if additional data is difficult to obtain post-COVID crisis.

Table 10. Overall power to detect a difference in rate of meeting primary endpoint in CAPTURE group vs usual care, assuming 5% performance rate in usual care; 67 total practices; 10 CAPTURE+/practice

| Improvement over usual care | +7.5% | +10% | +15% | +25% | +50% |
|-----------------------------|-------|------|-------|-------|-------|
| ICC=0.05 | 0.76 | 0.92 | >0.99 | >0.99 | >0.99 |

| | | | | | |
|----------|------|------|------|-------|-------|
| ICC=0.10 | 0.65 | 0.84 | 0.98 | >0.99 | >0.99 |
| ICC=0.15 | 0.55 | 0.76 | 0.95 | >0.99 | >0.99 |

However, we have important secondary analyses that include determining whether care is improved for patients who have spirometrically defined COPD. Based on data accumulated to date, we have a prevalence of roughly 2 spirometrically defined COPD patients per practice. These subsequent calculations demonstrate that based on 2 COPD patients/practice but with otherwise similar assumptions to Table 6, we would not be well powered for small effect sizes. Hence, while we would have important usable data should the study be unable to continue, the returns on investment made to date are far from fully realized. We strongly believe that all attempts should be made to complete the study as planned if we want to have the impact originally intended for this study, namely understanding whether screening benefits undiagnosed patients with COPD.

Table 11. Overall power to detect a difference in rate of meeting primary endpoint in CAPTURE group vs usual care, assuming 5% performance rate in usual care; 67 total practices; 2 COPD/practice

| Improvement over usual care | +7.5% | +10% | +15% | +25% | +50% |
|-----------------------------|-------|-------|------|------|-------|
| ICC=0.05 | <0.50 | <0.50 | 0.69 | 0.95 | >0.99 |
| ICC=0.10 | <0.50 | <0.50 | 0.67 | 0.95 | >0.99 |
| ICC=0.15 | <0.50 | <0.50 | 0.65 | 0.94 | >0.99 |

14 Reporting Conventions

P-values ≥ 0.001 will be reported to 3 decimal places; p-values less than 0.001 will be reported as " <0.001 ". The mean, standard deviation, and any other statistics other than quantiles, will be reported to one decimal place greater than the original data. Quantiles, such as median, or minimum and maximum will use the same number of decimal places as the original data. Estimated parameters, not on the same scale as raw observations (e.g., regression coefficients) will be reported to 3 significant figures.

14.1 Changes from Protocol-Planned Analyses

The following describes additional analyses that were not described in the protocol (Version 3.0, 26 September 2019) or modifications of protocol-specified analyses. These changes reflect advances in our knowledge since the design of the study in 2018 that were not incorporated as protocol amendments, but were discussed during the formation of the Statistical Analysis Plan. These changes were made prior to the database lock.

14.2 New SARS-COV-2 Inspired Analyses

The SARS-COV-2 pandemic has affected patient and practice enrollment and will potentially affect practice patterns moving forward. As part of the next protocol revision, the CAPTURE study plans to collect additional SARS-COV-2 inspired patient and practice information. This is a placeholder to update analyses once the next version of the protocol is complete. Of particular note will be analyses of additional data collected in response to SARS-COV-2 and analyses studying trends of 12-month outcomes that account for calendar time of collection

Protocol: N/A

SAP: 10.2.1 Secondary analyses of primary outcome

Additional sensitivity analyses will be conducted to assess the influence of the SARS-COV-2 pandemic on primary and secondary analyses. For the purpose of these analyses, we assume that participants who have completed their 12-month visit by March 19, 2020 provided baseline and 12-month follow-up measures that were unaffected by SARS-COV-2. We define an indicator variable SARS-COV-2=0 if a participant's baseline and 12-month follow-up measures were unaffected by SARS-COV-2 or SARS-COV-2=1 if participant's baseline or 12-month follow-up measures were affected by SARS-COV-2. All primary and secondary analyses will be repeated in the two cohorts defined by SARS-COV-2=1 or SARS-COV-2=0.

Protocol: N/A

SAP:10.2.2 Efficacy analyses of secondary outcomes**15 References**

1. Gosset, W.S. [Student, pseud.] 1908. The probable error of a mean. *Biometrika* 6: 1-25.
2. Pearson, K. 1900. On the criterion that a given system of deviations from the probable in the case of a correlated system of variables is such that it can be reasonably supposed to have arisen from random sampling. *Philosophical Magazine*, Series 5, 50: 157-175
3. Fisher, R.A. 1935. The logic of inductive inference. *Journal of the Royal Statistical Society*, Series A, 98: 39-54.
4. Liang, K.-Y. and Zeger, S.L. (1986) Longitudinal data analysis using generalized linear models. *Biometrika*, 73, 13-22.
5. Fitzmaurice, G. M., Laird, N. M., and Ware, J. H. (2011). *Applied Longitudinal Analysis* (2nd ed.) Hoboken, NJ: John Wiley and Sons.
6. Van Buuren, S. (2018). *Flexible Imputation of Missing Data* (2nd ed.) Boca Raton, FL: CRC Press.
7. Van Buuren, S., and Groothuis-Oudshoorn, K. (2011). mice: Multivariate Imputation by Chained Equations in R. *Journal of Statistical Software*, 45(3), 1-67. URL <https://www.jstatsoft.org/v45/i03/>.

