4. Pre-bronchodilator spirometry will be done for all participants. Post-bronchodilator spirometry will be performed for participants with abnormal spirometry ($FEV_1/FVC < 0.70$ or $FEV_1 < 80\%$ predicted) *If the participant has taken a bronchodilator within a 2-hour window of spirometry the spirometry will be considered post-bronchodilator and a pre-bronchodilator spirometry will not be done.
5. The 12-month assessment consists of patient reported data, collected by the COPD Foundation, and medical record review completed by site coordinators.
6. This will be completed in those that are smoking at V1.

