9.4 Covariates and Subgroups

The effect of the CAPTURE intervention will be explored in predefined subgroups of interest with results tabulated (estimated difference in average proportion of CAPTURE+ patients per practice meeting composite endpoint between intervention arms by subgroup, corresponding 95% confidence interval and p-value) as well as displayed via forest plots. These analyses will proceed similarly to that described for the primary endpoint in section 11.1. Individual-level covariates used to define subgroups of interest are categorical age (45-59 years, 60-69 years, 70-80 years), gender (Male, Female), race (American Indian/Alaska Native, Asian, Native Hawaiian or Other Pacific Islander, Black or African American, White, Unknown or Not Reported), ethnicity (Hispanic/Latino, Non-Hispanic/Latino, Unknown or Not Reported), educational status (Less than High School Graduate, High School Graduate/GED, Vocational/Some College, College Degree, Professional/Graduate Degree, or Not Reported), insurance status (private, public, none), living arrangements (alone, not alone), employment status (working, not working, unknown), smoking status (Current, Former, Never), asthma history, baseline respiratory medications (short-acting bronchodilator, maintenance respiratory medication, or none), cardiac morbidity, COPD Assessment Test (CAT) score (10 or above versus less than 10), BMI (Below 25.0 [Normal/Underweight], 25.0-29.9 [Overweight], 30.0-39.9 [Obese], 40.0 and Above [Severely Obese]), as well as cohorts defined in section 6.1 (Spirometrically Defined COPD, Clinically Significant COPD, Mild COPD, No COPD by Spirometry, PRISm, and SNO). Practice level covariates include practice type (Part of large health system/ACO/similar, Part of academic medical center/health system, Federally Qualified Health Care Center, Independent practice, Other), location (Rural, Non-rural), being a residency site, having in-house spirometry, and number of MD/DO/NP/PA primary care clinicians (0-4, 5-9, 10 or More). Because of the possible impact of the SARS-CoV-2 pandemic on study outcomes, these analyses will be repeated in subgroups defined by whether the one-year follow-up period had entirely elapsed by March 19, 2020 (date when PBRNs paused study enrollment due to SARS-CoV-2); that is, the analyses will be repeated separately in the cohort with baseline visit completed on or before March 19, 2019, and separately in the cohort with baseline visit completed after March 19, 2019. Chart review and patient follow-up survey need not be completed by March 19, 2020 for a patient to be categorized as having pre-pandemic follow-up for this subgroup analysis.

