
9.5 Missing Data

Baseline data, except for spirometry measurements, are expected to have few or no missing values. Baseline spirometry measurements are expected to be missing for a small portion of patients due to patient refusal/inability, administration error, or spirometry measurements having insufficient quality. Data from the 12-month medical record review are expected to be missing for a small portion of patients (among those selected for follow-up) due to various problems accessing the medical record. Data from the 12-month patient survey are expected to be missing for a significant portion of patients due to patients not returning completed surveys.

Any missing data or data anomalies will be communicated to the site(s) for clarification/resolution. We will summarize the extent of missing data by intervention group. Patient demographics, other baseline characteristics, and available 12-month follow-up data will be compared between those with and without complete follow-up data, among those who were prospectively selected for follow-up, overall and by intervention group.

The primary analysis of the primary and secondary endpoints will be among those with complete follow-up (complete data for the relevant portions of both the chart review and follow-up survey).

For each Aim 3 endpoint that is collected via both medical record review and patient survey, sensitivity analyses will be conducted by imputing missing outcome data using different assumptions and applying the primary analysis method to the resulting data sets. Sensitivity analyses will include

1. Imputation of negative responses (i.e., responses indicating that the outcome has not occurred) for all missing patient survey responses, followed by analysis of all patients with medical record review data
2. Imputation of positive responses (i.e., responses indicating that the outcome has occurred) for all missing patient survey responses, followed by analysis of all patients with medical record review data; and
3. Multiple imputation of all missing outcome data using the observed outcomes and covariates, as described below, followed by analysis of all patients selected for follow-up.

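### SAP 9.4 and 14.2 define the pre-pandemic cohort by different rules, and the leftover 14.2 rule sorts patients by when data were collected, not by when follow-up took place

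*SAP*

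**What the plan says.** SAP 9.4 asks whether a patient's one-year follow-up had fully elapsed by 19 March 2020, the date enrolment paused. It turns that into a baseline date: "the analyses will be repeated separately in the cohort with baseline visit completed on or before March 19, 2019", set against those with a later baseline. It adds: "Chart review and patient follow-up survey need not be completed by March 19, 2020 for a patient to be categorized as having pre-pandemic follow-up".

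SAP 14.2 attaches the same calendar date to a different event: "we assume that participants who have completed their 12-month visit by March 19, 2020 provided baseline and 12-month follow-up measures that were unaffected". That is the only criterion given for its pandemic indicator. It continues: "All primary and secondary analyses will be repeated in the two cohorts defined by SARS-COV-2=1 or SARS-COV-2=0". It also says of itself: "This is a placeholder to update analyses once the next version of the protocol is complete".

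Three other places bear on this:
- SAP 5.1, Table 1, lists the Aim 3 endpoints by pandemic cohort among the secondary endpoints. The cohorts are to rest on enrolment date and on how far the pandemic may have touched follow-up.
- SAP 7.5, footnote 5: "The 12-month assessment consists of patient reported data, collected by the COPD Foundation, and medical record review completed by site coordinators".
- SAP 9.5 restricts the main analysis of each endpoint to patients with "complete data for the relevant portions of both the chart review and follow-up survey".

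**The concern.** The two rules serve one purpose with one cut-off, yet 9.4 expressly sets aside the criterion that 14.2 adopts. Nothing ranks them. SAP 11.2 runs the primary and secondary outcomes in the 9.4 subgroups, and 14.2 repeats all primary and secondary analyses in its own cohorts. Two sets of pandemic-cohort results are therefore authorised for the Aim 3 endpoints.

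The 14.2 rule is also the weaker one on its merits. Whether care was affected by the pandemic depends on when the 12 months of care took place. It does not depend on when a survey came back or a coordinator opened the chart. A rule based on completion date selects on response speed or on abstraction scheduling, and a comparison of its two cohorts would mix those with any pandemic effect.

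**Working it through.** **Inputs.** Cut-off 19 March 2020 (SAP 9.4 and 14.2). Contact window 365 ± 30 days, stated for the patient contact C2 only (SAP 7.5). Survey counts at 25 March 2020 (SAP 13.1, Table 9). Abstraction start dates (SAP 13.1, Table 8).

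**1. Reproduce Table 9.** Eligible: 118 + 256 + 6 = 380. Completed: 84 + 134 + 30 = 248. Rate: 248 / 380 = 65.3%, which matches the stated 65%. Not completed: 380 − 248 = 132 (34.7%). Of these, 20 were lost to follow-up, so 132 − 20 = 112 were still outstanding.

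**2. If the visit in 14.2 means the survey contact only.**
- The unaffected cohort can hold at most 248 of the 380. The count is dated six days after the cut-off, so 248 is an upper bound.
- Patients wrongly left out: a baseline of 18 February 2019 reaches day 395 on 19 March 2020. Any baseline from 19 February to 19 March 2019 can therefore be surveyed within the window but after the cut-off. Such a patient is pre-pandemic under 9.4 and not unaffected under 14.2. The same holds for an earlier baseline with a late or unreturned survey.
- Patients wrongly let in: 19 March 2020 − 335 days = 19 April 2019, and 19 March 2020 − 365 days = 20 March 2019. A baseline from 20 March to about 19 April 2019 can be surveyed early, by the cut-off, and be labelled unaffected. For a 19 April 2019 baseline, day 365 is 18 April 2020, so up to about 30 days of the outcome year fall after the cut-off. Section 9.4 puts all these patients in the later cohort.

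**3. If the visit includes chart review, as footnote 5 says of the 12-month assessment.** Table 8 gives the "Original ideal date of starting for 12- month medical records abstraction":

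| PBRN | Start | Days after 19 March 2020 |
|---|---|---|
| A | 23 March 2020 | 4 |
| B | 30 March 2020 | 11 |
| E | 6 April 2020 | 18 |
| C, D | unknown | not determinable |
| F | no eligible patients until September 2020 | none under either rule |

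On those planned dates A, B and E contribute about no one to the unaffected cohort.

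**4. Fit with the missing-data plan.** SAP 9.5 and 11.2 repeat the analyses with missing survey responses imputed. On either reading, a patient who never returned a survey did not complete the visit by the cut-off. The 14.2 unaffected cohort then has no unreturned surveys to impute, so those sensitivity analyses lose much of their purpose there. Under 9.4 non-responders stay in the cohort.

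**5. Which text is current.** SAP 4.1 says the SAP is written for protocol 7.0. SAP 14.1, which introduces 14.2, works from protocol 3.0. Section 14.2 points to SAP 10.2.1 and 10.2.2; section 10.2 now covers protocol deviations and has no subsections, and secondary efficacy analyses are in 11.2.

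**The case against.** The best reply is that the documents already show which rule operates. Section 14.2 is labelled a placeholder and is visibly out of date. SAP 11.2 refers to the 9.4 subgroups and never to 14.2, and 9.4 settles the point about data collection in so many words. This may be uncleaned text rather than two live designs. That is probably how it arose, but 14.2 still states in the future tense that all primary and secondary analyses will be repeated on its split, and no sentence withdraws it.

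It can also be said that the counts overstate the gap. The main method is complete-case, so patients who never return a survey drop out under 9.4 too. This stands. Within Table 9, on the survey-only reading, the complete-case difference is roughly those of the 112 outstanding who later responded, plus anyone who completed on 20 to 25 March. The 132 is not a like-for-like loss.

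Three stronger readings are tempting, and the documents do not support them:
- A reader might infer that 14.2 leaves the unaffected cohort nearly empty. That needs chart review to be part of the visit, whereas footnote 5 defines the assessment and the schedule separates the contact from the record review. It also rests on planned dates at three of the six PBRNs listed.
- A reader might add the early-survey mislabelling to the loss of patients at A, B and E. These need opposite meanings of *visit* and cannot both hold. The mislabelling is also confined to about a month of baselines.
- A reader might infer that the rule could be chosen after unblinding. Both analyses are prespecified, 14.2 calls its own a sensitivity analysis, and SAP 9.1 and 9.2 require the SAP and its decisions to be settled first.

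**Conclusion.** The inconsistency is real and more than clerical, because the two rules classify patients differently and one classifies on the wrong basis. Section 14.2 leaves out patients with a wholly pre-pandemic outcome year when their survey or chart review was late or missing. On the survey-only reading it can also admit patients whose outcome year ran up to about 30 days past the cut-off.

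Its size depends on an undefined word. Survey only: at most 248 of 380 eligible at 25 March 2020. Survey plus chart review: about none from A, B and E on planned dates, with C and D unknown. The documents do not give the size of the 9.4 cohort. The 380 are survey-eligible followed patients, not CAPTURE+ patients alone, so no ratio of the two cohorts and no power figure can be derived.

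The reach is limited to the secondary, subgroup and sensitivity analyses by pandemic cohort. The primary test in SAP 11.1 does not use either rule and is unaffected.

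**What to change.** Delete the cohort definition and its indicator variable from SAP 14.2. State once that all pandemic-cohort analyses, including the repeated primary and secondary analyses, use the baseline-date rule in 9.4. That rule follows the period of care and agrees with the enrolment-date basis in SAP Table 1 and the protocol endpoint. Remove the placeholder sentence and the references to SAP 10.2.1 and 10.2.2 at the same time.

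If a second definition is wanted on purpose, label it as a separate sensitivity analysis, name 9.4 as governing, and say whether the 12-month visit means the survey, the chart review or both.

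The cost is SAP wording only. No new data are needed, since baseline visit dates are already held.
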